7.3 Risk/benefit assessment

7.3.1 Benefits

Study subjects will have no direct benefit from study participation. However, subjects will receive a free health check-up and there is a potential future societal benefit should the outcome of this study lead to a subsequent vaccination and challenge study resulting in a vaccine able to prevent TD caused by ETEC.

7.3.2 Risks

Risks Associated with ETEC Infection: The main risk is also the primary objective in this study: diarrhea caused by ETEC. Infection with ETEC can cause profuse watery diarrhea, abdominal cramping, abdominal pain, malaise, headache, urgency of defecation, lightheadedness and/or dehydration. Fever, nausea with or without vomiting, chills, loss of appetite, muscle aches and bloating can also occur but are less common. Illness develops 1-3 days after exposure and usually lasts 3-4 days [29] without treatment, but generally improves within 24 hours of antibiotic therapy.

In order to reduce the risk of secondary infection after discharge, all subjects in the study will receive a 3-day course of antibiotics starting no later than Day 6. Ciprofloxacin is the first-line antibiotic treatment for all subjects. If a subject is unable or unwilling to take ciprofloxacin, azithromycin or amoxicillin will be used instead. The risk of diarrhea complications will be minimized by a conservative approach to timing of antibiotic administration, well within an interval that has been shown to be efficacious, as well as daily clinical monitoring. Stool output will be closely monitored.

Risks Associated with Post-Infectious Irritable Bowel Syndrome (PI-IBS): Recent studies also suggest an increased risk of post-infectious irritable bowel syndrome (PI-IBS) following bacterial enteritis, and infection with ETEC has been found to be associated with these sequelae. A long duration (>2 weeks) of TD has been shown to be a risk factor for development of PI-IBS [30]. Prompt treatment of the ETEC infection, as done in the present study, cuts the duration of

any ETEC illness short and thus most likely eliminates the risk of PI-IBS. Symptoms of PI-IBS will be screened for with the Functional Bowel Disorder Survey (FBS) administered on study day 180. A study provider will review each FBS. Any participant identified as having a risk for PI-IBS will be referred for follow-up care. PI-IBS may be detected in 3-17% of people who experience travelers diarrhea (TD) [9], however there have been no documented cases of PI-IBS in enteric challenge study participants [31].

Risks Associated with Antibiotics: Therapeutic antibiotics for use in this study are licensed, approved medications that have been used extensively, and shown to be very safe with only rare side effects. The most commonly reported side effects for ciprofloxacin are gastrointestinal symptoms (nausea, vomiting, and diarrhea) in as many as 5 persons in 100. Other reported symptoms in less than 1 person in 100 include rash, dizziness, and headache. Rarely, allergic reactions to these medications have been observed. Ciprofloxacin is not recommended for use in pregnancy due to concerns of joint damage to the unborn child (based on studies in young animals). Pregnancy is exclusionary for study participation and is documented through testing prior to study interventions and provided discussion on methods to prevent pregnancy during study. Fluoroquinolones, including ciprofloxacin, are associated with an increased risk of tendonitis and tendon rupture in all ages. The risk of developing fluoroquinolone-associated tendonitis and tendon rupture is further increased in older patients, usually over 60 years of age, in patients taking corticosteroid drugs, and in patients with kidney, heart, or lung transplants, all of whom are excluded from this study. *Clostridium difficile*-associated diarrhea (CDAD/ pseudomembranous colitis) has been reported with use of nearly all antibacterial agents.

Subjects will not be discharged until they are well and have had at least two consecutive stool cultures negative for the challenge strain. Both stool cultures may be from the same day. Approximately 6 months after challenge, all subjects will have a follow-up contact by telephone to inquire about the occurrence of any new chronic illnesses or serious adverse events.

Risks Associated with SARS-CoV-2 Exposure and Risk Mitigation: The risk that the COVID-19 pandemic will influence the possibility to perform the study according to plan, or influence the results of the study, will be continuously assessed by the study team. Since the subjects are planned to be enrolled in Q1 2024, when a majority of the adult US population will have been vaccinated or infected with SARS-CoV-2, the risk that the pandemic will have major influence on the study is deemed to be small.

It is the intent of the Center for Immunization Research (CIR) to mitigate risk and provide a safe environment for participants while they are inpatient on the unit during the study. The CIR will educate and encourage all potential study volunteers to be fully vaccinated with one of the COVID licensed/EUA vaccines prior to enrolling in this study. Volunteers will not be required to be vaccinated against SARS-CoV-2, however, vaccinated volunteers will be prioritized for enrollment.

The CIR will follow recommendations from the CDC when implementing clinical trials. The CIR will also follow institutional guidelines and policies. Current recommendations include vaccination with one of the licensed/EUA vaccines for all adults.

Volunteers will be educated on the risks of not being vaccinated. They will sign a disclaimer regarding vaccination status and possible exposure to the virus. Volunteers will be strongly encouraged to wear a mask and maintain social distance from others.

Depending on the level of COVID illness in the community and current CDC and JHU guidelines, volunteers may be asked to obtain a COVID-19 test 1-5 days prior to admission. All volunteers will be screened for symptoms and tested on arrival to the unit on the day of inpatient admission. Potential volunteers who test positive for SARS-CoV-2 will not be eligible for enrollment.

Risks Associated with Venipuncture and IV fluid administration: Blood sampling of study participants may cause pain at the time of sample collection and may result in the development of bruising, bleeding, lightheadedness, syncope (rarely) and infection (rarely). Intravenous catheters may additionally infiltrate and cause swelling and/or discomfort.

Risks Associated with Stool Collection: There are no risks associated with the collection of stool samples. However, participants may be asked to provide up to three rectal swabs per inpatient day as needed. Risks of using rectal swabs could include mild discomfort, embarrassment, and (very rarely) bleeding or irritation.

Risks Associated with Transmission of Challenge strain: This *ETEC* strain has the potential for risk to both the environment and to the research personnel; however, the risk to the environment in regard to potential transmission outside of the CIR facility is low. The risk to the environment will be reduced by:

- ensuring that all human waste products from inpatients are disinfected with bleach prior to disposal,
- emphasizing the importance of handwashing for participants and staff,
- ensuring proper disposal/cleaning of linen,
- ensuring participants will not be discharged until they are no longer shedding the challenge strain, as per procedures outlined in the protocol.

Risks Associated with Isolation: Volunteers may feel bored or anxious about not being able to leave the unit or being separated from family, friends, and community while they are on the unit. The unit will be staffed 24/7 with medical staff and overnight with security staff. There will be planned activities in which the subjects can participate. There are big screen TVs throughout the unit as well as games, and a kitchen and dining area.

Risks Associated with Laboratory Results: There may be physical, psychological, and social risks if participants test positive for hepatitis B, hepatitis C, and/or HIV. Participants testing positive will be counseled and referred for treatment.

Risks Associated with Breach of Confidentiality: All data and medical information obtained about participants will be considered privileged and held in confidence. A breach of confidentiality in which private health information is made public is possible. Participants will not be identified by name in any published report/presentation of the results. The Sponsor, their delegates, and the FDA may inspect the records of this research as part of their responsibility to oversee research and ensure protection of participants. Study results and data may be published in scientific/medical journals; the identity of individual participants will not be disclosed.

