The study will consist of three study periods: screening, in-patient period and out-patient follow-up. Subjects will be evaluated for study eligibility during the screening period. After provision of written informed consent, subject eligibility for study entry will be assessed. Subjects who have been assessed eligible for the study, based on screening evaluations, will be admitted to the in-patient unit on Day -1, the day before E24377A administration, for study orientation and to be monitored for any signs and symptoms of illness. At baseline (Day 1), subjects who will remain eligible and willing to participate will be enrolled in the study and receive a single administration of E24377A. Subjects may remain in the in-patient unit until Day 9 (routine discharge is scheduled for 8 days after challenge dependent upon 2 consecutive negative stool culture results). During in-patient period, subjects will be examined on a daily basis for signs and symptoms of ETEC illness. Vital signs will be measured at least 3 times daily starting on Day 1, and postural blood pressure and pulse will be measured as needed. All stools will be collected and evaluated, weighed, and graded by the study staff. Up to 3 stools and/or rectal swabs each day will be cultured.

If the subject develops any symptom suggestive of diarrhea, they will be encouraged to drink liquids. If a subject vomits or is unable to consume an adequate volume of liquids, then intravenous (IV) fluids will be administered.

In order to reduce the risk of secondary infection after discharge, all subjects will receive a 3-day course of antibiotics. The subject will begin a 3-day course of ciprofloxacin 500 mg by mouth twice daily (or azithromycin 500 mg by mouth daily for three days, or amoxicillin 500 mg by mouth three times daily for three days if the subject was allergic to ciprofloxacin) on the morning of Day 6, or sooner if the subject has met the criteria for early antibiotic treatment (see Section 9.4.8.2.)

Subjects will be discharged from the in-patient unit if determined eligible for discharge. Subjects who meet the criteria for early antibiotic treatment, may be discharged from the in-patient unit earlier than anticipated upon meeting discharge criteria. Discharge criteria include at least 2 stools negative for the challenge organism, having taken at least 2 doses of antibiotics, and have improvement or resolution of symptoms.

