9 INVESTIGATIONAL PLAN

This is an open label study with the aim to estimate the incidence of moderate and severe diarrhea among participants challenged with 4×10^9 cfu of the *E. coli* E24377A strain. [REDACTED]

The study will be conducted at one site; the Center for Immunization Research, Johns Hopkins Bloomberg School of Public Health in Baltimore, Maryland, United States.

Up to 30 (minimum 25) subjects will be enrolled and challenged with approximately 4×10^9 cfu of the *E. coli* E24377A strain.

Overall description of study design

The study will consist of three study periods: screening, inpatient period and outpatient follow-up. Subjects will be evaluated for study eligibility during the screening period. After provision of written informed consent, subject eligibility for study entry will be assessed. Subjects who have been assessed to be eligible for the study, based on screening evaluations, will be admitted to the in-patient unit on Day -1, the day before E24377A administration, for study orientation and to be monitored for any signs and symptoms of illness. At baseline (Day 1), subjects who remain eligible and are willing to participate will be enrolled in the study and receive a single administration of E24377A.

Subjects may remain in the in-patient unit until they meet discharge criteria, see Section 9.4.8.2. Routine discharge is scheduled for Day 9, dependent upon 2 consecutive negative stool culture results. During the in-patient period, subjects will be examined daily for signs and symptoms of ETEC illness. Vital signs will be measured at least 3 times daily starting on Day 1, and postural blood pressure and pulse will be measured as needed. All stools will be collected and evaluated, weighed, and graded by the study staff. Up to 3 stools and/or rectal swabs collected each day will be cultured.

If the subject develops any symptom suggestive of diarrhea, they will be encouraged to drink liquids. If a subject vomits or is unable to consume an adequate volume of liquids, then intravenous (IV) fluids may be administered.

In order to reduce the risk of secondary infection after discharge, all subjects will receive a 3-day course of antibiotics. The subject will begin a 3-day course of ciprofloxacin 500 mg by mouth twice daily (or azithromycin 500 mg by mouth daily for three days, or amoxicillin 500 mg by mouth three times daily for three days if the subject was allergic to or unwilling to take

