ciprofloxacin per the PI discretion) on the morning of Day 6, or sooner if the subject has met the criteria for early antibiotic treatment (see Section 9.4.8.2).

Subjects will be discharged from the in-patient unit if determined eligible for discharge (2 stools negative for the challenge organism by culture, having received at least 2 doses of antibiotics, with improvement or resolution of symptoms). Subjects who meet the criteria for early antibiotic treatment, may be discharged from the in-patient unit prior to Day 9.

After discharge from the in-patient unit, all subjects will attend the scheduled follow-up visit/contact on an out-patient basis on Day 29 (physical visit) and Day 180 (phone).

The analyses for the exploratory endpoints may continue after the study database has been locked.

The timing and frequency of study visits and assessments are presented in the schedule of events in Table 1.

Table 1. Schedule of Events (Subject Visit Schedule and assessments)

	Study Specific Screen	Inpatient period										Out-patient visit	Phone call
Study Day	Scr -60 to -2	-1	1	2	3	4	5	6	7	8	9	29	180
Informed Consent and Comprehension Test	X												
Demographics	X												
Inclusion/Exclusion Criteria	X	X	X										
Medical History	X	X											
Functional Bowel Survey	X												X
COVID-19 Test		X											
Full Physical Exam	X	X											
Focused Physical Exam			X	X	X	X	X	X	X	X	X	(X) ¹	
Vital Signs ²	X	X	X	X	X	X	X	X	X	X	X		
Serology (HIV, HBsAg, and HCV)	X ³												
CBC w/diff	X	X ⁴											
Clinical Chemistry	X	X ⁴											
ABO Type	X												
IgA deficiency screen	X ³												
Serum HCG Pregnancy Test ⁵	X	X											
Urine Drug Screen	X												
Urine Pregnancy Test ⁵			(X)										X
Enrollment			X										
E24377A challenge			X										
Prior and concomitant medications	X	X	X	X	X	X	X	X	X	X	X		
Interim Medical Interview ⁶			X	X	X	X	X	X	X	X	X		X
AE			X	X	X	X	X	X	X	X	X		
SAE/AESI			X	X	X	X	X	X	X	X	X		X
Start Antibiotic therapy								X ⁷					
Stool collection for weighing and grading ⁸			X	X	X	X	X	X	X	X	(X)		
Stool culture ⁹			X	X ¹⁰	X	X ¹⁰	X	X	X	X	(X)		
Fecal samples for exploratory immunogenicity endpoints		X	(X) ¹¹	X	X	X	X	X	X	X	(X)		X
Blood Samples for exploratory Immunogenicity endpoints		X	(X) ¹¹		X	X				X			X

Whole blood for ALS/Memory B Cells/PaxGene		X	(X) ¹¹			X			X		X		
ETEC Impact on ADLs							X						
Planned Discharge										X ¹²			
Follow-Up Telephone Contact													X
Study Completion													X

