9.4.8.2 Concomitant therapy during the study

During the study, all subjects will receive a 3-day course of antibiotics.

On the morning of Day 6 (or sooner if the subject met the criteria for early antibiotic treatment; see below), all subjects will start a 3-day course of ciprofloxacin 500 mg BID.

Subjects with an allergy to or who are unwilling to take a fluoroquinolone, may receive azithromycin 500 mg by mouth daily for three days or amoxicillin 500 mg by mouth three times daily for three days.

If, because of illness, a subject is unable to take oral antibiotics, intravenous antibiotics may be given at an appropriate dose based on weight and clinical status.

Criteria for early antibiotic treatment

Subjects meeting any of the following criteria before Day 6 will start antibiotic treatment at that time:

- Severe diarrhea as defined as >800 grams of grade 3-5 stools within a rolling 24 hour-period (see Section 9.5.3.1.2).
- Stool output consistent with moderate diarrhea for 48 hours
- Diarrhea of any severity AND 2 or more of the following symptoms: severe abdominal pain, severe abdominal cramps, severe nausea, severe headache, severe myalgias, severe arthralgia), any fever ($\geq 100.4^{\circ}\text{F}$, 38.0°C), or any vomiting
- Any fever $\geq 102.1^{\circ}\text{F}$ (39.0°C)
- A study clinician determines early treatment is warranted for any other reason

Subjects who meet the criteria for early antibiotic treatment, may be discharged from the in-patient unit earlier than anticipated upon meeting discharge criteria. Discharge criteria include at least 2 stools negative for the challenge organism, having taken at least 2 doses of antibiotics, and have no or improved symptoms.

Subjects taking any other non-antibiotic medication on a chronic basis may continue with that medication unless directed otherwise by a study clinician. All such medication will be collected on admission to the inpatient facility and will be dispensed by study staff until discharge.

Rehydration

Subjects passing grade 3-5 stools post-challenge will be asked to drink liquids, at the same volume as their stool output.

A subject may be administered IV fluids if they:

- Experience abrupt onset of diarrhea, defined as passage of an initial loose/liquid stool of >300 g, or >400 g of loose/liquid stools over 2 hours in conjunction with other symptoms, as determined by PI or designee.

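### The discharge list in Protocol 9.4.8.2 and its repeats leave out 'consecutive' from the two-negative-culture rule that 7.3.2 sets for every subject

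*Protocol*

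**What the plan says.** Protocol 7.3.2 states a bar that applies to all subjects: "Subjects will not be discharged until they are well and have had at least two consecutive stool cultures negative for the challenge strain". The next sentence allows both cultures to come from one day.

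The text on routine discharge agrees. The synopsis says "routine discharge is scheduled for 8 days after challenge dependent upon 2 consecutive negative stool culture results", and section 9 says "Routine discharge is scheduled for Day 9, dependent upon 2 consecutive negative stool culture results". Section 9.3.2 (compensation) likewise treats a subject without two consecutive negatives as not yet eligible to leave by Day 9.

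The list of discharge criteria is in 9.4.8.2, in the paragraph on subjects who qualify for early antibiotics. It requires "at least 2 stools negative for the challenge organism, having taken at least 2 doses of antibiotics, and have no or improved symptoms". Section 9 points there: "Subjects may remain in the in-patient unit until they meet discharge criteria, see Section 9.4.8.2". Section 9.3.8 does the same. The list recurs in the synopsis ("Discharge criteria include at least 2 stools negative for the challenge organism, having taken at least 2 doses of antibiotics") and in section 9, where it stands in parentheses as the meaning of eligibility for discharge ("2 stools negative for the challenge organism by culture, having received at least 2 doses of antibiotics, with improvement or resolution of symptoms"). The parenthesis in 9.3.8 mentions only two negative stools. None of these says *consecutive*.

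**The concern.** Release from the unit is a transmission-control decision. Among the measures limiting environmental risk, 7.3.2 lists "ensuring participants will not be discharged until they are no longer shedding the challenge strain, as per procedures outlined in the protocol". Someone looking for those procedures would most naturally follow the cross-references to 9.4.8.2, which has the looser wording. The stricter sentence is in the risk section, in the text under antibiotic risks.

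The two wordings part for a subject who has two negative cultures with a positive between them. The list also sets no limit on the time between the two negatives. Literally, then, an isolated early negative, a run of positives and one later negative would satisfy its culture condition. The gap matters most for subjects released before Day 9 after early antibiotics, because 9.4.8.2 is the list given for them and 9.5.6.7 sends no stool cultures after early discharge.

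**Working it through.** The plan gives no figure to reproduce. The check is a comparison of the places where the two documents state the discharge culture rule.

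| Place | Subject of the text | *Consecutive*? |
|---|---|---|
| Protocol 7.3.2 | all discharges | yes |
| Protocol synopsis | routine discharge | yes |
| Protocol section 9 | routine discharge | yes |
| Protocol 9.3.2 | not eligible by Day 9 | yes |
| SAP 2.1 | routine discharge | yes |
| Protocol 9.4.8.2 | discharge criteria | no |
| Protocol synopsis | discharge criteria | no |
| Protocol section 9 | eligibility for discharge | no |
| Protocol 9.3.8 | discharge criteria, citing 9.4.8.2 | no |
| SAP 2.1 | eligibility for discharge | no |
| SAP 2.6.4 | discharge criteria | no |

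Five statements have the word and six do not. The synopsis, section 9 and SAP 2.1 each contain both forms.

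**Where the rules differ.** Write N for a negative culture and P for a positive one.

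- Three cultures: 2^3 = 8 orders. At least two N: NNN, NNP, NPN, PNN (4). Two N in a row: NNN, NNP, PNN (3). Only NPN passes the list and fails 7.3.2: 1 of 8.
- Four cultures: 2^4 = 16 orders. Those with at least two N but no two in a row are NPNP, NPPN and PNPN: 3 of 16.

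The count depends on how many cultures are considered, and it is not a probability. Orders are not equally likely. Under Table 1 footnote 9 culturing stops after two negatives in a row, so some of the longer orders would seldom be observed. The enumeration shows only that the rules are not equivalent.

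**How many subjects come under the list.** Protocol Table 3 reports early antibiotics in 8 subjects (50%) of 16 in one earlier study of this lot, and in 12 of 15 in another. The 15 equals the number with moderate or severe illness among that study's 20 subjects, so if nobody else was treated early the rate is 12/20 = 60%. Assuming 50% to 60% here, with 25 to 30 subjects challenged:

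- low: 0.50 × 25 = 12.5
- high: 0.60 × 30 = 18

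So about 13 to 18 subjects might be treated early. That is the number for whom early discharge could arise, not the number wrongly discharged. The latter needs a rate of alternating cultures, which the documents do not give.

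**The case against.** The strongest reply is that there is no real conflict. Section 7.3.2 is mandatory and makes no exception for early-treated subjects. The lists in 9.4.8.2, the synopsis and SAP 2.6.4 say that the criteria *include* the named items, so they need not be complete, and both texts are satisfied by following 7.3.2. Section 9 requires two consecutive negatives for routine discharge in the sentence right after it cites 9.4.8.2. Footnotes 8 and 9 to Table 1 end weighing and culturing at two negatives in a row, so the unit already tracks that pattern. Under 9.5.6.7 an investigator must find the subject eligible before early discharge.

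Most of this stands as evidence of intent: the protocol very probably means consecutive. It does not remove the inconsistency. The parenthesis in section 9 gives the list as what eligibility means, without *include*, and 9.3.8 also gives its criterion without that word. The footnotes govern when culturing and weighing stop, not who may leave.

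A reader might infer more than the texts support:

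- **That the protocol lets shedding subjects go home.** It does not; 7.3.2 forbids it. The transmission safeguard refers only to procedures in the protocol and names no section, so 7.3.2 is as much its source as 9.4.8.2.
- **That *well* in 7.3.2 should be relaxed to the symptom wording of 9.4.8.2.** Nothing shows that 9.4.8.2 should prevail on symptoms, and the change would loosen a safety statement covering everyone.
- **That the SAP wording creates an analysis problem.** SAP 2.1 and 2.6.4 describe the design; they do not govern discharge.

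**Conclusion.** The point holds as a minor internal conflict, probably a drafting omission. A subject with cultures negative, positive, negative is barred from discharge by 7.3.2 and meets the culture condition in 9.4.8.2, and no culture after early discharge would reveal the difference. The conclusion rests on reading the list literally; staff who read it together with 7.3.2 would apply the stricter rule. The investigator's eligibility decision and the remaining antibiotic doses dispensed at early discharge limit any harm. The number of subjects affected cannot be estimated from the documents. The primary attack-rate estimate is unaffected: neither the endpoint definition nor the full analysis set refers to the discharge culture rule.

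**What to change.** In Protocol 9.4.8.2, state the culture condition as: *at least 2 consecutive stool cultures negative for the challenge strain (may be from the same day)*. Keep the antibiotic-dose and symptom conditions there as they are. Bring the discharge lists in the synopsis and section 9, and the parenthesis in 9.3.8, to the same wording, or replace them with a reference to 9.4.8.2. SAP 2.1 and 2.6.4 can be aligned at the next revision as housekeeping. Leave *well* in 7.3.2 unchanged.

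The cost is one revised phrase in 9.4.8.2 and matching edits to its repeats. No cultures are needed beyond those Table 1 footnote 9 already requires, since it continues culturing until two in a row are negative. An occasional early-treated subject may stay until one more negative culture: after negative, positive, negative, the next negative completes the pair. Routine Day 9 discharge does not change.
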